7.8.3. Vital Signs

Vital signs data will be summarized descriptively for the safety population by study visit and by measurement time, if applicable. Reported values and changes from baseline in weight, BMI, temperature, systolic and diastolic blood pressure, heart rate, and respiratory rate will be summarized. The number and percentage of subjects with markedly abnormal vital signs, as defined below, will be summarized. Abnormalities of interest include:

- American Heart Association categories for hypertension:
 - Elevated: systolic blood pressure of ≥120 to ≤129 mmHg with diastolic blood pressure <80 mmHg
 - Stage 1 Hypertension: systolic blood pressure of ≥130 to ≤139 mmHg or diastolic blood pressure of ≥80 to ≤89 mmHg
 - Stage 2 Hypertension: systolic blood pressure of ≥140 mmHg or diastolic blood pressure of ≥90 mmHg
 - Hypertensive Crisis: systolic blood pressure of>180 mmHg and/or diastolic blood pressure of>120 mmHg
- Heart rate (beats per minute, bpm):
 - Abnormally low: a decrease from baseline of ≥ 15 to a value ≤ 50 bpm
 - Abnormally high: an increase from baseline of ≥ 15 to a value ≥ 120 bpm
- Temperature (°C):
 - Abnormally high: value ≥38.3°C and ≥0.8°C increase from baseline.
- Respiratory rate (bpm):
 - Abnormally low: <12 breaths/min

Abnormally high: >25 breaths/min

All vital signs including the reported values for each parameters and overall interpretations will be listed by subject.

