5.2. Exclusion Criteria

Subjects are excluded from the study if any of the following criteria apply:

1. Life-threatening or organ system-threatening SLE activity that is sufficiently active that it is expected to require increase in treatment during the study.

- 2. Proteinuria consistent with nephrotic syndrome (i.e., \geq 3.5 grams proteinuria/day, estimated based on UPCR \geq 350 mg/mmol) at Screening.
- 3. Active lupus-related neuropsychiatric disease at Screening or Baseline (i.e., Day 1 prior to randomization), as defined by the central nervous system portion of SLEDAI-2K 30 or BILAG 2004 (with the exceptions of mild stable lupus headache, fatigue, mild stable organic brain syndrome).
- 4. Drug-induced lupus.
- 5. Any serious health condition, which, in the opinion of the Investigator or Sponsor, would place the subject at undue risk from the study or would confound interpretation of safety or efficacy outcomes, including, but not limited to:
 - a. Uncompensated congestive heart failure as defined by New York Heart Association Class III or IV.
 - b. Clinically significant active cardiac disease (e.g., unstable angina or acute myocardial infarction ≤ 3 months prior to first dose of study drug).
 - c. Clinically relevant or significant ECG abnormalities at Screening, including ECG with QTcF; in subjects with ventricular conduction delay (QRS > 120 msec), cardiologist consultation and discussion with, and agreement of, Medical Monitor is required for participation.
 - d. Active cerebrovascular disease (e.g., stroke or transient ischemic attack) \leq 3 months prior to first dose of study drug, unless attributed to SLE disease and stable on treatment.
 - e. Uncontrolled hypertension, defined by a persistent systolic blood pressure > 160 mmHg or diastolic blood pressure > 100 mmHg.
 - f. Uncontrolled diabetes.
 - g. Known clinically significant immunodeficiency.
 - h. Current or recent (within the past 12 months) history of alcoholism or significant drug abuse (recreational use of cannabis is not an exclusion criterion).
 - i. Elective major surgery anticipated to take place during the study period.
- 6. Recent serious or ongoing infection; risk or history of serious infection, including:
 - a. Active or latent TB (refer to §6.7 for specific requirements for TB screening).

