8. CLINICAL MANAGEMENT GUIDELINES AND REQUIREMENTS

8.1. Clinical Management of Adverse Events of Interest

8.1.1. Infusion-Related Reactions

Guidelines for assessing, grading, and reporting IRRs are provided in §9.8 and §9.8.1.

No infusion reactions were observed following single or repeated IV infusions of ALPN-101 in a previous study in healthy volunteers. The incidence and nature of ALPN-101-related IRRs, if any, remain uncharacterized. Based on experience with other immunomodulatory compounds, including approved CD28 pathway inhibitors, IRRs may include hypersensitivity reactions (e.g., anaphylaxis) and/or cytokine release syndromes. IRRs typically present with dizziness, headache, circulatory (hypo- or hypertension), respiratory (cough, wheezing, dyspnea), mucocutaneous (flushing, urticaria, pruritis, rash), and abdominal (nausea, vomiting, cramps, diarrhea) symptoms. Symptoms typically begin during or within 24 hours of drug administration.

If any subject experiences an infusion reaction, including anaphylaxis or cytokine release syndrome:

- Monitoring frequency and duration will be increased, and will continue until episode is resolved.
- Supportive care will be initiated per institutional guidelines. This may include, but is not limited to, slowing and/or interruption of the current infusion; administration of antihistamines such as diphenhydramine or loratadine; administration of antipyretics such as acetaminophen or paracetamol; administration of corticosteroids; IV fluid support such as normal saline; vasopressors; anti-rigor medication such as meperidine.
- Using the kits provided by the central laboratory, blood will be collected for assessment of serum levels of mast cell tryptase and quantitative IgE; blood should be collected as soon as possible after initiation of the event, and repeated at 60 minutes and following resolution or discharge from care for the event. In addition, a serum sample for exploratory analysis of chemokines and cytokines should be collected.

In the event that an IRR occurs when the subject is not in the clinic, all subjects should undergo an unscheduled visit as soon as possible (< 24 hr).

Table 3 Guidelines for Management of IRRs

AE Grade	ALPN-101 Dose Modification	Toxicity Management		

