3.2. Safety Endpoints

The primary study objective of assessing safety and tolerability of ALPN-101 will be evaluated using the endpoints listed in below:

- Treatment-emergent adverse events (TEAEs), treatment-emergent adverse events of interest (AEIs; infusion-related reactions, oral mucocutaneous lesions, infections grade ≥3), and serious adverse events (SAEs)
- Abnormal laboratory test results and observed and change/shift from baseline in over time for:
 - Chemistry
 - Hematology
 - Coagulation
 - Urinalysis
- Abnormal vital signs results and observed and change/shift from baseline over time for:
 - Systolic and diastolic blood pressures (mmHg)
 - Heart rate (bpm)
 - Respiratory rate (bpm)
 - Body temperature (°C)
 - Weight (kg)
- Abnormal electrocardiogram (ECG) parameters and observed and change/shift from baseline over time for:
 - Heart rate (bpm)
 - QT interval (msec)

- PR interval (msec)
- ORS duration (msec)
- RR interval (msec)
- QTcB interval (msec)
- QTcF interval (msec)

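### The blood pressure abnormality table in SAP 7.8.3 ignores baseline, lets categories overlap and has no low-pressure category

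*SAP*

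**What the plan says.** SAP 7.8.3 plans a categorical summary: "The number and percentage of subjects with markedly abnormal vital signs, as defined below, will be summarized". The blood pressure categories begin with "Elevated: systolic blood pressure of ≥120 to ≤129 mmHg with diastolic blood pressure <80 mmHg" and continue with "Stage 1 Hypertension: systolic blood pressure of ≥130 to ≤139 mmHg or diastolic blood pressure of ≥80 to ≤89 mmHg" and "Stage 2 Hypertension: systolic blood pressure of ≥140 mmHg or diastolic blood pressure of ≥90 mmHg". A fourth category, hypertensive crisis, lies above 180 systolic and/or 120 diastolic. All four use the observed reading alone.

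Other items in the same list are built differently. For heart rate the upper rule is "Abnormally high: an increase from baseline of ≥ 15 to a value ≥ 120 bpm", with a matching low rule that also uses baseline. The temperature rule requires a rise from baseline. Respiratory rate has a low and a high limit without a baseline term.

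SAP 3.2 defines the vital-sign endpoint as "Abnormal vital signs results and observed and change/shift from baseline over time for" a list that includes systolic and diastolic pressure. SAP 7.8.3 provides changes from baseline in the continuous values, by visit and measurement time, and a by-subject listing. It specifies no shift table for blood pressure categories.

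Protocol 5.2 excludes only "Uncontrolled hypertension, defined by a persistent systolic blood pressure > 160 mmHg or diastolic blood pressure > 100 mmHg". Protocol 8.1.1 gives "circulatory (hypo- or hypertension" among the typical signs of infusion-related reactions.

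**The concern.** Safety is the primary objective, and Protocol 10.5.5 makes the incidence of clinically significant vital-sign abnormalities a safety endpoint. The rule above is the only categorical blood pressure analysis in SAP 7.8.3. It has four weaknesses.

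- **Pre-existing values count.** The entry limit of 160/100 admits subjects already in Elevated, Stage 1 or Stage 2. They are counted with no change on treatment.
- **The categories overlap.** No rule assigns a reading to one category.
- **There is no low side.** A post-infusion fall cannot be counted, although the protocol anticipates one and measures vital signs about 10 minutes after each infusion.
- **The counting rule is missing.** SAP 7.8.3 does not say whether the count is per visit or at any time, or whether pre-dose Day 1 readings are excluded. SAP 7.8.2 does state an any-time rule for liver tests.

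The label also fits poorly: 120 to 129 mmHg systolic is reported as markedly abnormal.

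**Working it through.** **Overlap.** Take 145/85. Diastolic 85 lies in 80 to 89, so Stage 1 is met through its 'or'. Systolic 145 is at least 140, so Stage 2 is met as well. Stage 2 has no upper bound, so it also contains every Crisis reading.

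**Number of readings.** Protocol Table 1 has two vital-sign measurements at each of 12 dosing visits and one each on Days 169 and 197. Removing the Day 1 pre-dose baseline gives 12 × 2 − 1 + 1 + 1 = 25.

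**Other domains.** SAP 7.8.2 defines treatment-emergent laboratory abnormality as grade 0 at baseline and grade 1 to 4 afterwards. SAP 7.8.2 also shifts urinalysis from baseline to worst post-baseline, and SAP 7.8.4 uses QTcF increases from baseline and an ECG shift table. Blood pressure is the exception.

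**Size with no drug effect.** The plan states no expected flag rate, blood pressure mean or SD, so there is no figure to reproduce. The rates below are simulated (60,000 subjects per scenario, bivariate normal, correlation 0.65, subject means truncated at 160/100, 25 post-baseline readings). All distributions are assumptions. Entries are % of subjects; the last four columns use the worst post-baseline reading.

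| Mean SBP/DBP (SBP between/within SD; DBP between/within SD) | In a category at baseline | Any category | Stage 2 as written | Worse category than baseline | New Stage 2 or higher |
|---|---|---|---|---|---|
| 108/67 (9/5; 6/4) | 14.8 | 48.0 | 1.9 | 40.9 | 1.8 |
| 112/70 (10/6; 7/5) | 29.9 | 73.6 | 13.2 | 62.3 | 11.6 |
| 116/73 (11/7; 7/5) | 44.8 | 87.0 | 29.0 | 71.3 | 24.0 |
| 120/76 (12/8; 8/6) | 58.6 | 94.5 | 54.4 | 73.4 | 41.0 |
| 128/80 (14/9; 9/6) | 75.1 | 98.1 | 76.2 | 63.9 | 46.2 |

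At a single post-baseline reading, the any-category rate is 15% to 75%, the same range as at baseline.

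**Response to a rise.** With +10/+5 mmHg, the any-category rate moves from 94.5% to 99.1% at 120/76 and from 73.6% to 94.1% at 112/70. The written Stage 2 row moves from 54.4% to 79.8% and from 13.2% to 40.0%.

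A second assumed model (120/75, SDs 12/8 systolic and 8/6 diastolic, correlation 0.6) with +5/+3 mmHg gives, on worst reading:

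- any category: 94.5% to 97.8%, or 3.3 points (0.033 × 38 = about 1 subject per arm, with 76/2 = 38);
- Stage 2 as written: 53% to 68%, 15 points;
- new Stage 2 or higher: 40% to 55%, 15 points;
- any worse category than baseline: 74.5% to 81.5%, 7 points.

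**Response to a fall.** With −10/−6 mmHg at 120/76, the any-category rate drops from 94.5% to 78.5%. The fall shows only as fewer high readings. No row counts it.

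**The case against.** Three stronger conclusions are tempting, and the documents do not support them.

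*Nearly every subject will be flagged.* This needs any-time counting and a combined any-category row. SAP 7.8.3 states neither; it lists four categories and speaks of summaries by visit and measurement time. It also needs a mean systolic pressure of about 120 or more. Lower assumed pressures give 48% to 87% even with any-time counting.

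*A pressor effect would barely move the table.* That is true of the combined row only. The written Stage 2 row responds about as strongly as a new-Stage-2 row (15 points each above). Baseline referencing therefore separates emergent from pre-existing values without adding sensitivity.

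*Falls in pressure are lost.* They are lost to this table, not to the analysis. Changes from baseline are summarised by visit and time, and SAP 7 requires minimum and maximum. Every reading is listed. Protocol 9.8.1 has each sign of an infusion reaction recorded as its own adverse event.

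It is also fair to say that safety is descriptive, that no decision rule uses this table, and that SAP 3.2 already names shift from baseline.

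What remains is that means and extremes do not give a count. If two of 38 subjects each fell by 40 mmHg, the arm mean would move by 2 × 40 / 38 = 2.1 mmHg, and the minimum would show one value rather than how many subjects fell.

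**Conclusion.** The point holds for the categorical blood pressure table and no further. The lack of a baseline term, the overlap, the missing low side and the unstated counting rule can all be read directly from SAP 7.8.3 and need no assumptions.

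The size does rest on assumed distributions. About 15% to 75% of subjects would already be in a category at baseline. With any-time counting over 25 readings, about half to nearly all would be flagged with no drug effect. As written, the table mixes background blood pressure with change on treatment, and it omits the shift from baseline that SAP 3.2 names. This is a cheap improvement to a descriptive safety table; it does not undermine the safety analysis as a whole.

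**What to change.** Amend SAP 7.8.3 as follows.

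1. Assign each reading to its single highest category: Normal, Elevated, Stage 1, Stage 2 or Crisis.
2. State the counting window: post-baseline readings only, by visit and measurement time, and worst post-baseline.
3. Present a shift table by arm of baseline category against worst post-baseline category, which implements SAP 3.2.
4. Keep the markedly abnormal label for new Stage 2 or higher in subjects below Stage 2 at baseline. Do not make any worse category the headline count, since it flags about 41% to 74% with no drug effect on a worst-reading basis.
5. Add a prespecified low-pressure row with a baseline term, split by pre- and post-infusion time, as a reporting threshold only. Protocol Table 4 contains a figure (systolic below 90 mmHg or a fall of more than 30% from baseline), but there it is an anaphylaxis criterion tied to a known allergen. The sponsor should confirm the threshold.

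The cost is a few lines of SAP text and one reprogrammed table, with no new data. Subjects already at Stage 2 at baseline leave the headline count and appear only in the shift table. Subtracting the last column of the table above from the Stage 2 column puts the loss at 13.2 − 11.6 = 1.6 points at 112/70, 54.4 − 41.0 = 13.4 at 120/76 and 76.2 − 46.2 = 30.0 at 128/80.

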Any		Manage per institutional standards at the discretion of Investigator. Monitor subjects for signs and symptoms of IRR (e.g., fever and/or shaking chills, flushing and/or itching, alterations in heart rate and blood pressure, dyspnea or chest discomfort, or skin rashes) and anaphylaxis (e.g., acute onset of generalized urticaria, angioedema, wheezing, hypotension, or tachycardia).		
1	The infusion rate may be decreased by 50% or temporarily interrupted until resolution of the event.			
2	The infusion rate may be decreased 50% or temporarily interrupted until resolution of the event. Subsequent infusions, if applicable, may be given at 50% of the initial infusion rate	acetaminophen, NSAIDs, or meperidine per institutional standard prior to subsequent doses Steroids should not be used for routine premedication of Grade ≤ 2 infusion reactions		
3	Consult with Medical Monitor or Sponsor	Stop infusion. Manage per institutional standards (e.g., oral or parenteral corticosteroids, antihistamines, antipyretics, meperidine) Premedication per institutional standard prior to subsequent doses Consider hospitalization.		
4	Permanently discontinue	Stop infusion. Hospitalize. Manage severe infusion-related reactions per institutional standards (e.g., IM epinephrine, followed by IV diphenhydramine and ranitidine, and IV glucocorticoid).		

AE, Adverse event; IM, Intramuscular; IRR, Infusion-related reaction; IV, Intravenous; NSAIDs, Nonsteroidal anti-inflammatory drugs.

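### SAP 7.8.3 counts markedly abnormal blood pressure only in the high direction, so measured low blood pressure has no pre-specified count by arm

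*SAP*

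**What the plan says.** SAP 7.8.3 ties its count of outliers to a list of definitions: "The number and percentage of subjects with markedly abnormal vital signs, as defined below, will be summarized". The blood-pressure entry in that list is "American Heart Association categories for hypertension", with four levels: elevated, stage 1, stage 2 and crisis. The list also has a low and a high limit for heart rate, a low and a high limit for respiratory rate, and a high limit for temperature. The section then adds a listing: "All vital signs including the reported values for each parameters and overall interpretations will be listed by subject".

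SAP 3.2 sets the safety endpoint without a direction. It names "Abnormal vital signs results and observed and change/shift from baseline over time for" several measures, and systolic and diastolic pressure come first.

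Protocol 8.1.1 explains why low pressure is of interest. Its list of typical infusion-reaction signs covers both directions: "IRRs typically present with dizziness, headache, circulatory (hypo- or hypertension". It also says: "The incidence and nature of ALPN-101-related IRRs, if any, remain uncharacterized". Table 3 tells sites to watch for blood-pressure changes and for "anaphylaxis (e.g., acute onset of generalized urticaria, angioedema, wheezing, hypotension, or tachycardia".

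**The concern.** The protocol expects a reaction to this drug to be able to move blood pressure either way, and it treats a fall as a warning sign of anaphylaxis. The table meant to pick out abnormal measured values looks only upward. It will report, by arm, how many subjects had mildly raised pressure, and it will report nothing about how many had low pressure.

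What is at stake is one incomplete set of rows in a table that serves the primary objective. If low readings occur, the count would have to be made afterwards from the listing, with a limit chosen once the data are in hand.

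**Working it through.** The plan gives no figure to reproduce here. The check compares texts and adds simple counting.

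**1. Definitions in SAP 7.8.3.** Blood pressure 4 (all high) + heart rate 2 (one low, one high) + temperature 1 (high) + respiratory rate 2 (one low, one high) = 9. Definitions for low blood pressure: 0.

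**2. The rules applied to example readings (mmHg).**

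| Reading | Category under SAP 7.8.3 |
|---|---|
| 145/92 | Stage 2 |
| 122/70 | Elevated |
| 89/59 | none |
| 85/50 | none |
| 80/40 | none |
| 70/35 | none |

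**3. Readings not checked against a low limit.** Protocol Table 1 schedules vital signs before and about 10 minutes after each of 12 infusions, and once each on Day 169 and Day 197.
- Per subject: 12 × 2 + 2 = 26. Removing the Day 1 pre-dose baseline leaves 25, of which 12 are post-infusion and 13 are other readings.
- SAP 4.1 gives 76 enrolled. With full attendance: 25 × 76 = 1,900 readings, and 12 × 76 = 912 post-infusion.
- Assuming an even split, 76/2 = 38 per arm: 25 × 38 = 950 readings and 12 × 38 = 456 post-infusion. One subject is 1/38 = 2.6% of an arm.

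**4. Whether the planned summaries would show the same thing.** Suppose each affected subject in an arm of 38 falls by 40 mmHg at the same time point. One such subject moves the mean change by −40/38 = −1.1 mmHg. Five (5/38 = 13.2%) move it by −200/38 = −5.3 mmHg. The minimum shows the single lowest value, not how many subjects were low.

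**5. A usable limit.** The adult blood-pressure criterion in protocol Table 4 is a systolic value below 90 mmHg or a fall of more than 30%. The percentage part adds to the absolute part only when the reference systolic value is above 90/0.70 = 128.6 mmHg. Above that, the reference has to be stated. With Day 1 baseline 130, same-visit pre-infusion 150 and post-infusion 100:
- against the pre-infusion value, (150 − 100)/150 = 33.3%, flagged;
- against the Day 1 baseline, (130 − 100)/130 = 23.1%, not flagged.

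**The case against.** The strongest reply is that low pressure that matters clinically is already captured. The protocol synopsis and section 4.4.4 include clinically significant vital-sign changes among adverse events. Infusion reactions are events of interest, reported within 24 hours with a narrative, and section 9.8.1 asks for each sign to be recorded separately with its severity. SAP 7.8 and 7.8.1 summarise adverse events by arm. SAP 7.8.3 also summarises pressure by visit and measurement time. The minimum is therefore shown, and a minimum of 90 mmHg or more means that nobody was below 90 at that time point. Temperature too has only a high limit, and the list of abnormalities is worded as a selection.

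These points are right, and they keep the matter small. They do not supply the missing count. Adverse-event capture depends on the investigator reporting the reading, and SAP 7.8.1 names examination, laboratory and ECG findings as analysed as adverse events but not vital signs. A minimum shows whether the count below 90 is zero, not what it is otherwise. High pressure, heart rate and fever have the same adverse-event route, yet the SAP still counts them against limits. If the list is read as open-ended, it still states no low limit.

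Some criticism of the remedy also stands. The Table 4 limit was written for exposure to a known allergen, so its use here is a reviewer's choice that the sponsor should confirm. It is systolic only, so an isolated low diastolic value stays uncounted. An absolute cut-off will flag a subject who drifts from 91 to 89, although the SAP's own low respiratory-rate limit has the same form.

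**Conclusion.** The concern holds, as a minor one. SAP 7.8.3 has nine definitions, four for blood pressure and none for low pressure, although SAP 3.2 sets the endpoint without a direction and the protocol names hypotension as a reaction sign. Safety is analysed descriptively, so no estimate, test or error rate changes, and no data are lost. The gap is confined to a by-arm threshold count of measured low values, including those not reported as adverse events.

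The reading counts assume full attendance, and the per-arm figures assume an even split of the 76. Neither the number of low readings nor the share that would go unreported can be derived from the documents.

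**What to change.** Before unblinding, add one low-pressure category to SAP 7.8.3: systolic below 90 mmHg, or a systolic fall of more than 30%. Describe it as a flag, not as a diagnosis of anaphylaxis.

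- **Counts:** subjects by arm (a) with the flag at any post-baseline reading and (b) with the flag at a post-infusion reading.
- **Reference for the 30% fall:** for post-infusion readings, the same-visit pre-infusion value, or the SAP 6.1 baseline if that is missing. For all other readings (pre-infusion, Day 169, Day 197, unscheduled), the SAP 6.1 baseline.
- **Denominator:** safety-population subjects with at least one such reading, following the rule in SAP 7.8.2 for laboratory values.

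The cost is a few lines of text and two rows in a planned table, from data already collected. Some incidental low readings will be counted in both arms, including in subjects whose usual systolic pressure is near 90 mmHg. The count supplements adverse-event reporting and does not replace it, because the scheduled post-infusion reading is a single time point about 10 minutes after the infusion ends.
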